### **14.11 Missing Data Handling**

The primary effectiveness analysis will be based on the FAS. If 5% of the data or fewer are missing for the analysis, no imputation will be used. Otherwise, missing data will be imputed for the FAS using multiple imputation (MI). The model variables used for the MI analysis may include baseline variables such as age, gender, and BMI. Ten imputations will be conducted and combined using the Rubin's rule. Sensitivity analysis will be performed using available data in both FAS and PPAS as well as tipping-point analysis in FAS to fully understand the missing data impact on the study results.

The primary safety analysis will be based on the FAS subjects with available data at 30-days, i.e. whose status (event, no event) at 30-days can be determined. No imputation will be conducted.

For the secondary and ancillary endpoints, analysis will be conducted with available data in FAS. No imputation will be conducted.

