The effectiveness hypothesis is to test if the surgical success rate is above the performance goal. The sample size for primary effectiveness is based on combined cohorts of inguinal and ventral. A performance goal of 85% (100%-conversion rate) is pre-defined to test the statistical hypothesis. Assuming a success rate of 93%, a sample size of 172 subjects for the combined inguinal and ventral hernia cohort will provide 90% of power with one-sided alpha of 0.025. Calculation was performed using the PASS 2023. Accounting for 10% attrition rate, the enrollment is 192 subjects with a hernia repair procedure.

The primary safety objective is also part of the consideration for the sample size determination. The primary safety endpoint is the rate of subjects with any procedure- and/or device-related SSEs from the first incision through 30 days post-procedure. The primary safety objective, assessed separately for each hernia cohort, is based on a performance goal of 30% and expected safety event rate of 15% for the cohort. A sample size of 86 will provide 86% power with a one-sided alpha of 0.0125 (Bonferroni Correction for hernia cohort). Calculation was performed using the PASS 2023. Accounting for 10% attrition rate, the enrollment is 96 per cohort or 192 total subjects with a hernia repair procedure.

An attrition rate of 10% was assumed to ensure an adequate sample for each objective, resulting in 192 total subjects (96 per hernia cohort).

Endpoint	Performance Goal	Expected Study Rate	Minimum Sample Size	Minimum Power	Minimum Alpha
Primary Effectiveness	85%	93%	172	90%	0.025
Primary Safety	30%	15%	86	86%	0.0125

The secondary objectives will be assessed using descriptive statistics and no sample size assessment was made for these objectives.

7. Statistical Methods

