7.4 Handling of Missing, Unused, and Spurious Data and Dropouts

The primary effectiveness analysis will be based on the FAS. If 5% of the data or fewer are missing for the analysis, no imputation will be used (Buhi, Jakobsen). Otherwise, missing data will be imputed for the FAS using multiple imputation (MI). Unless model errors dictate otherwise, the model variables used for the MI analysis will include baseline variables age, gender (1=female, 0=male), and BMI; the model will also include a variable for hernia cohort (inguinal=1, ventral=0). Ten imputations will be conducted and combined using the Rubin's rule (Rubin) after 100 burn-in iterations. The estimate and variance of the mean proportion of subjects considered a surgical success will be determined for each imputation dataset. For the primary objective, the mean and variance for the proportion will be determined using MI analysis methods and the objective will be tested using a Z-test comparing the observed surgical success rate to the primary objective performance goal of 85%. The seed will be defined as the date of the database snapshot in the format YYYYMMDD.

Sensitivity analysis will be performed for the primary effectiveness objective using available data in both FAS and PPAS as well as tipping-point analysis in FAS to fully understand the missing data impact on the study results.

The primary safety analysis will be based on FAS subjects with available data at 30-days, i.e. whose status (event, no event) at 30-days can be determined. For the secondary and ancillary endpoints, analysis will be conducted with available data in FAS. No imputation will be conducted for these analyses. Additional clarification for determining data availability at 30 days:

- Subjects with a 30-day visit at least 30 days post-procedure have complete/available 30-day data
- For subjects whose 30-day visit occurred within the visit window between 23 and 29 days post-procedure, these subjects will be considered as have been followed through 30 days and their event status will be determined using any events that occurred through 30 days post-procedure, even if occurring after the 30-day visit
- Subjects who did not complete a 30-day visit will be considered to have available data in the following scenarios:
 - 1) if the subject completed zero follow-up visits and has a relevant event in the 30 days following the procedure, the subject will be included in the analysis as having the event;

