 - 2) for subjects without a relevant event and who missed the 30-day visit but had some other post-procedure visit within the 30-day visit window or at anytime after the 30-day window (e.g., a completed 3-month visit), the subject will be included in the analysis as not experiencing the event. Visits and discontinuations after the 3-month visit will not be considered under this provision.

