7.5 Adjustments for Multiple Comparisons

For the primary effectiveness endpoint, one hypothesis will be tested at an alpha of 0.025 one-sided. If the one-sided primary objective p-value is <0.025 , then the null hypothesis will be rejected, and the test will be declared statistically significant.

After the primary effectiveness objective is met, the primary safety objective for each hernia cohort will be tested. For the primary safety endpoint (procedure- and/or device-related SSE rate), the closed test procedure (Holm's method, i.e. Holm-Bonferroni method) will be used to protect the overall study-wise error rate for hernia cohorts (inguinal hernia and ventral hernia), thereby maintaining an overall type I error of one-sided of 0.025 for these objectives. To assess statistical significance of these objectives, the one-sided p-values will be determined and ordered from smallest to largest. First, the smaller p-value will be compared to 0.0125. If the p-value is larger than 0.0125, both tests will be considered non-significant. If the smaller p-value is less than 0.0125, the test will be considered significant and the larger p-value will be assessed; the larger p-value is then assessed with a p-value below 0.025 resulting in a determination of statistical significance for the larger p-value.

Secondary objectives and ancillary objectives are intended to be descriptive only. No multiplicity adjustment will be applied.

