7.9.2.6 Determination of Subjects/Data for Analysis

The analysis set for the primary safety objective will be FAS with available data at 30 days, i.e., those subjects whose status (event, no event) at 30 days can be determined. Data availability for assessments through 30 days will follow the logic described in section 7.4. The inguinal hernia cohort and ventral hernia cohort will be analysed separately.

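### Read literally, SAP 7.4 leaves out a subject with an SSE by day 30 who missed the 30-day visit but attended later, and keeps the same subject without an SSE as a non-event

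*SAP*

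**What the plan says.** Both documents restrict the primary safety analysis to FAS subjects whose event status at 30 days can be determined. Protocol 14.11 puts it as "The primary safety analysis will be based on the FAS subjects with available data at 30-days", with no imputation, and SAP 7.4 repeats the principle.

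SAP 7.4 then clarifies what counts as available data. For subjects who did not complete a 30-day visit it lists two scenarios:

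- Scenario 1: "if the subject completed zero follow-up visits and has a relevant event in the 30 days following the procedure". The subject is included as an event.
- Scenario 2: "for subjects without a relevant event and who missed the 30-day visit but had some other post-procedure visit", either within the 30-day window or after it, with the 3-month visit as the example. The subject is included as a non-event. Visits after the 3-month visit do not count.

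SAP 7.9.2.6 carries this into the primary safety objective: "Data availability for assessments through 30 days will follow the logic described in section 7.4". SAP 7.9.3 and 7.9.4 do the same for the 30-day secondary and ancillary endpoints. SAP 7.9.2.2 dates an SSE by the AE start date, not by a visit.

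Multiple imputation and a tipping-point analysis are specified for effectiveness only (SAP 7.4 and 7.9.1.7.1).

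**The concern.** Among subjects who miss the 30-day visit but are seen later, the list makes inclusion depend on the outcome. Without an SSE the subject enters the denominator. With an SSE the subject appears in neither scenario and, if the list is programmed as written, leaves numerator and denominator together. The event is not unknown: AEs are collected through day 30 whatever their relatedness (Protocol 12.1), and the CEC adjudicates SSEs (Protocol 13.1).

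The literal rule also makes the result depend on the snapshot date. An SSE counts while the subject has no follow-up visit and stops counting once a 3-month visit is completed.

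At stake is the per-cohort test against the 30% performance goal in a single-arm pivotal study, where a few events near the limit decide the outcome.

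**Working it through.** **Inputs from the documents.** The safety objective "is based on a performance goal of 30% and expected safety event rate of 15% for the cohort" (SAP section 6, Determination of Sample Size), with 86 evaluable per cohort, 86% power and one-sided alpha 0.0125. "Accounting for 10% attrition rate, the enrollment is 96 per cohort or 192 total subjects with a hernia repair procedure". Holm's procedure (SAP 7.5): "First, the smaller p-value will be compared to 0.0125", and the larger p-value then to 0.025. The test is binomial against 30% (SAP 7.9.2.5).

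**Assumed inputs.** m is the number per cohort who miss the 30-day visit but attend later, and z is the number with no follow-up visit at all. The documents give neither. I take m = 2, 5 or 10 of 96, z = 0 at first, and the same SSE risk in all subjects.

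**Step 1: reproduce the plan's power.** The largest c with P(X ≤ c | 86, 0.30) < 0.0125 is c = 16 (attained alpha 0.0118). P(X ≤ 16 | 86, 0.15) = 0.861, against 86% stated. Enrolment: 86/0.90 = 95.6, rounded up to 96. Both agree with the plan.

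**Step 2: fit the visit patterns to the list (no 30-day visit).**

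| Later visit up to 3 months | SSE by day 30 | Literal list |
|---|---|---|
| Yes | No | Kept as non-event (scenario 2) |
| Yes | Yes | In neither scenario |
| None | Yes | Kept as event (scenario 1) |
| None | No | In neither scenario |

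Row 2 lowers the rate and row 4 raises it. In row 2 the status is known; in row 4 it is not.

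**Step 3: direction for row 2.** If x events among n remain after k known events are dropped, restoring them gives (x + k)/(n + k) ≥ x/n. So the literal rule never gives a higher rate than a rule that keeps them.

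**Step 4: expected rate with z = 0.** Under the literal rule it is (96 − m)p / [(96 − m) + m(1 − p)].

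- p = 0.15, m = 2: 14.1/95.7 = 14.7%. m = 5: 13.65/95.25 = 14.3%. m = 10: 12.9/94.5 = 13.7%. The shift is 0.3 to 1.4 points.
- p = 0.30, m = 2, 5, 10: 29.6, 28.9, 27.7%.

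**Step 5: false-pass probability per test at a true rate of 30%.** Exact enumeration over the events among the m subjects, with the critical count recomputed for each resulting denominator (z = 0):

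| m of 96 | 0.0125 step | 0.025 step |
|---|---|---|
| 0 (full data) | 0.0088 | 0.0165 |
| 2 | 0.0121 | 0.0222 |
| 5 | 0.0177 | 0.0316 |
| 10 | 0.0288 | 0.0496 |

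With m = 2 both steps stay below nominal; with m = 5 both exceed it. Keeping the events returns the m = 0 row.

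**Step 6: add zero-visit subjects.** With m = 5 and z = 5 at p = 0.30, the literal expected rate is (86 × 0.30 + 5 × 0.30)/(86 + 3.5 + 1.5) = 27.3/91 = 30.0%, and the false-pass probabilities are 0.0090 and 0.0173, close to full data. With m = 2 and z = 8 the expected rate is 31.4%, and they are 0.0039 and 0.0080.

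**Step 7: results near the limit.** 20/96 gives p = 0.029 and fails both steps; dropping two events in this pattern gives 18/94, p = 0.012, which passes at 0.0125. 17/86 gives p = 0.022 and fails at 0.0125; 15/84 gives p = 0.0082 and passes.

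**The case against.** The strongest reply is that silence is not an instruction. No sentence excludes these subjects. The governing principle includes anyone whose status can be determined, and the two scenarios are offered only as clarification of it. That stands: this is probably a drafting omission, and a programmer could go either way. It does not remove the problem, because the list is the operative detail for building the dataset. The independent programming in SAP section 8 can show that two programmers differ, but not which reading was meant.

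A reader might infer that the rule always favours passing. It does not. Subjects with no follow-up visit are kept only if they had an event, which pushes the rate up, and step 6 shows that this can cancel or outweigh the other effect. The net direction depends on a mix of visit patterns that the documents do not give.

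A reader might also take the planned 10% attrition as the share of subjects in this pattern, and so read 2.9% and 5.0% as the expected false-pass rates. The documents do not support that. The Protocol synopsis uses the 10% for subjects without an assessed safety endpoint, whereas event-free late attenders are assessed under scenario 2. The pattern is narrowed further because SAP 7.4 accepts a 30-day visit at day 30 or later with no stated upper limit, and Protocol 10.1.4 allows phone or video contact in extreme circumstances.

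The step 7 examples are chosen at the boundary. At the ventral literature rate of 4.5% (SAP 7.9.2.4) the pass probability is 1.000 to three decimals under either rule.

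Finally, an available-case safety analysis without imputation is openly stated in both documents, and Protocol 14.2 permits sensitivity analyses for missing data. That is a disclosed choice, separate from the gap in the list. A required safety table is an addition, not the correction of an error.

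**Conclusion.** The point holds on the literal wording. The list in SAP 7.4 omits one visit pattern whose event status is known, contradicts the principle that it is meant to clarify, and treats the same visit pattern without an SSE as a non-event. Within that pattern the effect can only lower the SSE rate. The SAP does not support a claim that the whole rule is biased downward.

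The size is conditional on assumed frequencies of 2 to 10 of 96 per cohort, equal SSE risk and no zero-visit subjects. On those assumptions the false-pass probability at a true rate of 30% is 1.2 to 2.9% at the 0.0125 step and 2.2 to 5.0% at the 0.025 step, against 0.9% and 1.7% with full data. At the planned 15% the shift decides only results close to the limits of 16/86 and 17/86. That subjects with complications miss scheduled visits more often is plausible but not documented, and none of these figures uses it.

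It is worth settling before the snapshot, because the ambiguity concerns known primary safety events and the repair is short.

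**What to change.** Reword scenario 1 in SAP 7.4 so that any FAS subject with a qualifying SSE starting on or before day 30 is counted as an event, whatever visits were completed. Keep scenario 2 for non-events. The 30-day secondary and ancillary endpoints inherit the change through their reference to SAP 7.4.

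The rewording leaves zero-visit non-events out, so a conservative, upward asymmetry remains. With m = 5 and z = 5 the expected rate under the reworded rule is 14.4/91.75 = 15.7% when the truth is 15%, and the pass probability at the 0.0125 step is 0.82, against 0.88 with full data. So add, per cohort, a sensitivity table for subjects with undetermined 30-day safety status, showing best case, worst case and tipping point, on the model of SAP 7.9.1.7.1. For example, 16/86 with 10 undetermined passes at 0.0125 (p = 0.0118). It still passes if 2 of the 10 had an SSE (18/96, p = 0.0088) and fails if 3 did (19/96, p = 0.0165).

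Cost: a reworded scenario in SAP 7.4, a short addition to SAP 7.9.2, one extra table per cohort, and possibly a slightly less favourable SSE rate than the literal reading would give.

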7.5 Adjustments for Multiple Comparisons

For the primary effectiveness endpoint, one hypothesis will be tested at an alpha of 0.025 one-sided. If the one-sided primary objective p-value is <0.025 , then the null hypothesis will be rejected, and the test will be declared statistically significant.

After the primary effectiveness objective is met, the primary safety objective for each hernia cohort will be tested. For the primary safety endpoint (procedure- and/or device-related SSE rate), the closed test procedure (Holm's method, i.e. Holm-Bonferroni method) will be used to protect the overall study-wise error rate for hernia cohorts (inguinal hernia and ventral hernia), thereby maintaining an overall type I error of one-sided of 0.025 for these objectives. To assess statistical significance of these objectives, the one-sided p-values will be determined and ordered from smallest to largest. First, the smaller p-value will be compared to 0.0125. If the p-value is larger than 0.0125, both tests will be considered non-significant. If the smaller p-value is less than 0.0125, the test will be considered significant and the larger p-value will be assessed; the larger p-value is then assessed with a p-value below 0.025 resulting in a determination of statistical significance for the larger p-value.

Secondary objectives and ancillary objectives are intended to be descriptive only. No multiplicity adjustment will be applied.

7.6 Demographic and Other Baseline Characteristics

Demographic summaries will include age (in years), sex, race/ethnicity, and BMI.

7.7 Treatment Characteristics

A descriptive data summary for surgical procedure characteristics and exposure to the study device will be provided. Summaries will be discussed in the study report.

7.8 Interim Analyses

No interim analysis is planned for this study.

7.9 Evaluation of Objectives

7.9.1 Primary Effectiveness Objective

The primary effectiveness objective of this study is to demonstrate that the Medtronic Hugo™ RAS system is effective when used in inguinal and ventral hernia repair. The primary objective on effectiveness is to demonstrate that the surgical success rate is greater than the pre-defined performance goal (PG). The surgical success is defined as the procedure not going into conversion due to failure of the Hugo™ RAS system. Conversion is defined as the switch from the robotic-assisted approach using the Hugo™ RAS system to laparoscopic, open surgery, or use of an alternative robotic-assisted system. Procedural steps that are usually performed without robotic assistance per standard of care, including but not limited to mesh insertion, suture needle removal, or tacking, are not considered a conversion and will not contribute to the primary effectiveness endpoint.

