### 5.2 Endpoints

#### 5.2.1 Primary Endpoints

The primary effectiveness endpoint is the surgical success rate defined as the procedure not going into conversion. Conversion is defined as the switch from the robotic-assisted approach using the Hugo™ RAS system to laparoscopic, open surgery, or use of an alternative robotic-assisted system.

Procedural steps that are usually performed without robotic assistance per standard of care, including but not limited to mesh insertion, suture needle removal, or tacking, are not considered a conversion and will not contribute to the primary effectiveness endpoint.

The primary safety endpoint is the overall rate of subjects with one or more study procedure- and/or device-related surgical-site events (SSEs), from the first incision through 30 days post-procedure. SSE is defined as the following complications:

*Medtronic Business Restricted*

- Surgical-site occurrence (SSO):
  - Bleeding, Hemorrhage: Requiring transfusion
  - Bowel Injury
  - Bowel Obstruction
    - Note: Functional obstruction associated with general anesthesia and/or pain killer drugs (opioids) is excluded for this endpoint
  - Cellulitis
  - Epigastric Vessel Injury
  - Symptomatic Hematoma: Requiring procedural intervention
  - Symptomatic Seroma: Requiring procedural intervention
  - Symptomatic Edema: Requiring procedural intervention
    - Note: Procedural intervention is defined as percutaneous drainage, wound opening or debridement, suture excision, or mesh removal (partial or total)
- Surgical-site infection (SSI): Infection occurring where the surgery took place, including superficial, deep, and organ space infections (standardized definition developed by the CDC)

The relatedness of the SSEs being classified as “procedure- and/or device-related” may include three scenarios: (1) only procedure-related SSEs, (2) only device-related SSEs, and (3) SSEs that are both procedure- and device-related. In this study procedure-relatedness refers to an AE that occurs due to the hernia repair procedure with the Hugo™ RAS system, and device-relatedness refers to an AE that results from the presence or performance (intended or otherwise) of the Hugo™ RAS system.

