7.9.1.2 Endpoint Definition and Derivation

Sites are asked if the procedure was completed according to the surgical plan (Yes/No). If the answer was “No”, the site reported what was not done per the surgical plan; if the site specifies “Converted”, then the surgery is identified as a conversion. Surgical success is defined as a surgery that has not involved a conversion.

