7.9.1.4 Rationale for Performance Criteria

To determine performance criteria, analyses were performed on available literature. Point estimates along with 95% and 99% predicted intervals were calculated to provide plausible ranges of potential effect sizes. Clinically meaningful margins and statistical precisions have been taken into account to determine the appropriate performance goals. The performance goal (PG) of 85% is derived on literature research (**Table 1**).

Table 1: Primary Effectiveness Endpoint – Performance Goal Determination

Primary Effectiveness Endpoint: Surgical Success Rate		
Surgery Type	Performance goal (PG)	Rationale
Inguinal and Ventral Hernia Repair	85%	The literature-based mean effect size for conversions is 1.5% with a 95% CI of 0.2% to 9.4%. The 95% prediction interval is 0.1% to 29.3%. A PG of 85% for the surgical success rate, equivalent to a 15% conversion rate, is set, which is aligned with the upper 95% CI with an added 5.6% margin and falls within the 95% prediction interval.

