7.11 Changes to Planned Analysis

There were no changes to the statistical analysis as compared to CIP V5.0.

-

8. Validation Requirements

The analysis of the primary objectives will be validated by Level I, in which the peer reviewer independently programs output and then compares the output with that generated by the original Statistical Programmer. The analysis of the secondary and ancillary objectives, as well as the main AE/PD summaries will be validated by at least Level II, in which the peer reviewer reviews the code; where appropriate, performs manual calculations or simple programming checks to verify the output.

9. References

Holm, S. (1979). A Simple Sequentially Rejective Multiple Test Procedure. *Scandinavian Journal of Statistics*, 6, 65-70.

Rubin DB. *Multiple Imputation for Nonresponse in Surveys*. New York: John Wiley and Sons; 2004.

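### One sentence in SAP 7.9.1 limits failures to conversions caused by the Hugo system, against every other definition of the primary effectiveness endpoint

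*SAP*

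**What the plan says.** Protocol 5.2.1 sets the endpoint without reference to cause: "The primary effectiveness endpoint is the surgical success rate defined as the procedure not going into conversion". The synopsis, protocol 14.4.1 and SAP 4.1.1 say the same, and all of the full definitions describe conversion by what the surgeon switches to (laparoscopy, open surgery or another robot), not by why.

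The opening paragraph of SAP 7.9.1 differs: "The surgical success is defined as the procedure not going into conversion due to failure of the Hugo™ RAS system". Its next sentence returns to the cause-free definition of conversion.

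SAP 7.9.1.2, the section headed as the endpoint definition and derivation, takes the site's entry of a conversion and concludes: "Surgical success is defined as a surgery that has not involved a conversion".

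The benchmark is also cause-free. SAP section 6 states: "A performance goal of 85% (100%-conversion rate) is pre-defined to test the statistical hypothesis". SAP 7.9.1.4 adds: "A PG of 85% for the surgical success rate, equivalent to a 15% conversion rate, is set".

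The protocol gives device-related conversions a separate, supportive place: a subgroup analysis in the synopsis and a summary in 14.4.1. SAP 7.11 then states: "There were no changes to the statistical analysis as compared to CIP V5.0".

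**The concern.** A confirmatory endpoint needs one definition, and this one has two. Under the 7.9.1 sentence, a procedure converted for a reason other than system failure is counted as a success and compared with a goal written as 100% minus the conversion rate. The numerator and the benchmark would then measure different things, and the difference always favours passing.

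The stakes are high because SAP section 5 makes the effectiveness objective a condition of study success, and SAP 7.5 tests safety only after effectiveness is met. The narrower reading also has no working rule. No section says who would attribute a conversion to system failure, or by what criteria. The events committee's remit in protocol 13.1 is serious adverse events, deaths and surgical-site events; conversions as such are not in it.

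**Working it through.** **Step 1. Set the definitions side by side.**

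| Place | What counts as a failure |
|---|---|
| Protocol synopsis, 5.2.1, 14.4.1 | Any conversion |
| SAP 4.1.1 | Any conversion |
| SAP 7.3 (site pooling) | Outcome coded 1 for success, 0 for converted |
| SAP 7.9.1, opening paragraph | Only a conversion caused by failure of the system |
| SAP 7.9.1.1 and 7.9.1.4 | Goal is 100% minus the conversion rate; 15% conversion is the null |
| SAP 7.9.1.2 (derivation) | Any site-reported conversion; no step assigns cause |
| SAP 7.9.1.7.1 (tipping point) | Conversion to another form of surgery, no cause given |

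Only one entry restricts cause.

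**Step 2. Reproduce the plan's figure.** Inputs from SAP section 6: goal 85%; "Assuming a success rate of 93%, a sample size of 172 subjects", which "will provide 90% of power with one-sided alpha of 0.025"; 10% attrition. Protocol 14.4.1 specifies an exact binomial test. With X the number of successes among n subjects, the test passes if X ≥ r, where r is the smallest count with P(X ≥ r | p = 0.85) ≤ 0.025.

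- n = 172: r = 156, so at most 16 failures. Size 0.0189 (at 17 failures the p-value would be 0.033). Power at 93% success: 0.904.
- 172 / 0.90 = 191.1, rounded up to 192.
- n = 192: r = 174, so at most 18 failures. Size 0.0147.

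The stated 172, 90% and 192 all reproduce, so the sample size is not in question.

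**Step 3. Apply the 7.9.1 sentence literally.** Fix the true conversion rate at the null value of 15%. Let f be the share of conversions attributed to failure of the system. Only those count, so the counted success rate is 1 − 0.15f and the chance of passing is P(X ≥ r | p = 1 − 0.15f). The documents do not give f; the values below are assumptions, shown as a range.

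| Share f | Counted success rate | P(pass), n = 172 | P(pass), n = 192 |
|---|---|---|---|
| 100% | 85.0% | 0.019 | 0.015 |
| 90% | 86.5% | 0.062 | 0.054 |
| 80% | 88.0% | 0.166 | 0.156 |
| 75% | 88.75% | 0.251 | 0.244 |
| 50% | 92.5% | 0.851 | 0.868 |
| One third | 95.0% | 0.994 | 0.996 |

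**Step 4. A concrete case.** Take 26 conversions in 172 subjects (15.1%). If all count, there are 146 successes and the one-sided p-value is 0.57: the test fails. If 10 of the 26 are put down to other causes, 16 failures remain and the p-value is 0.019: the same data pass.

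**The case against.** The best defence is that the sentence is a slip in an introductory paragraph. The operative rules sit in the numbered subsections below it, and the one headed for derivation counts every conversion. A programmer who follows 7.9.1.2 produces the protocol's endpoint, and then there is no inflation. The pooling coding and the tipping-point text agree with that reading. There are safeguards too: SAP section 3 requires changes and post-hoc analyses to be identified in the study report, protocol section 14 requires SAP approval before the database snapshot, and SAP section 8 requires independent programming of the primary analysis. The statement in 7.11 that nothing changed fits a slip better than a deliberate narrowing.

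Much of this stands. A reader might infer that 7.9.1 governs the test, so that the trial will be judged on system-failure conversions alone; 7.9.1.2 does not support that. A reader might also infer that the operating surgeon would decide the cause, but no section says who would. Nor can it be shown that the literature behind the goal counted conversions of every cause. Protocol 6.2.2 and Table 13 simply speak of conversions, without stating a restriction.

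What the defence does not do is remove the contradiction. Independent programming confirms that two people read the text alike; it does not settle which of two written definitions is the endpoint.

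**Conclusion.** The contradiction is real, verbatim and in the primary endpoint, and it should be resolved before analysis. It makes the endpoint ambiguous; it does not show that the narrower definition will be applied. A reader might infer that the definition is open to choice once results are known. The SAP's wording would permit an argument for either reading, but the reporting and approval rules limit such a switch, and nothing in the documents suggests one is intended.

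The size is conditional on two things: that the 7.9.1 sentence is followed in place of 7.9.1.2, and the share of conversions attributed to the system, which is assumed. At a 100% share nothing changes. At 90% the false-positive rate at n = 172 is already 0.062, about two and a half times the nominal 0.025, and it climbs steeply below that.

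**What to change.** In SAP 7.9.1, delete the last eight words of the disputed sentence, that is, everything after the word conversion. Every conversion in the full analysis set then counts as a failure whatever its cause, in agreement with protocol 5.2.1, SAP 4.1.1 and SAP 7.9.1.2, and the statement in SAP 7.11 becomes true on this point. Keep device-related conversions as the separate summary that protocol 14.4.1 plans.

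The cost is one phrase in a SAP revision. Sample size, data collection, hypothesis and test are untouched: size stays at 0.019 for 172 subjects (0.015 for 192), and power at 93% success stays at 0.904 for 172.
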